APPENDIX 6: SCHEDULE OF EVENTS

Assessment	Screeni ng		Cycl	les 1-2			Cycl	Cycles 9-12, 9-18 or 9-24				End of Cycle 4	of of of C1D1 Cycle Cycle Cycle and			C; or	25+ (13+, i (after -KRd	E O T 25	LTFU 26,27			
Day	-21 to -1	1	8	15	22	1	8	15	22	1	8	15	22					1	8	15	22		
Informed Consent ¹	X																						
Demographics and Medical History ²	X																						
Skeletal Survey ³	X																						
CT/PET ²⁸	X														(X)	(X)	X					X	
ECG ⁴	X																						
Echocardiogram ⁵	X																						
Physical Exam/ ECOG ⁶	X	X				X				X								Х				X	
Vital Signs ⁷	X	X	X	X	X	X	X	X		X		X						X				X	
Hematology ⁸	X	X	X8	X8		X	X	X		X		X						X				X	
Serum Chemistry ⁹	X	X	X ⁹	X ⁹		X	X	X		X		X						X				X	

Assessment	Screeni ng		Cycl	les 1-2			Cycl	les 3-8	es 3-8 Cycles 9-12, 9 or 9-24					End of Cycle 4	End of Cycle 8	End of Cycle 12	24 mo after C1D1 and yearly x4	Cycles 13+, 19+, or 25+ (after end of E-KRd)			end	E O T 25	LTFU 26,27
Day	-21 to -1	1	8	15	22	1	8	15	22	1	8	15	22					1	8	15	22		
Pregnancy Test ¹⁰	X	X		(X) 10	(X)	X				X								X				X	
Disease Assessment ¹¹																							
β2-microglobulin	X																						
SPEP and IFIX ¹²	X	X		X 12,13		X				X								X				X	
24 hour Urine: UPEP and IFIX ¹³ ;14	X	X		X 14		X				X								X					
SFLC	X	X		X		X				X								X				X	
Quantitative IgGs	X	X		X		X				X								X				X	
BM Aspirate/ biopsy, cytogenetics, FISH ¹⁵	X													X	X	X	X					X	X
BM aspirate sample for MRD analysis ¹⁶	X													X	X	X	X					X	X
Correlative Samples ¹⁷	X													X	X	X	X					X	

Assessment	Screeni ng		Cycl	les 1-2			Cycles 3-8				Cycles 9-12, 9-18 or 9-24			End of Cycle 4	End of Cycle 8	End of Cycle 12	24 mo after C1D1 and yearly x4	Cycles 13+, 19+, or 25+ (after end of E-KRd)			end	E O T 25	LTFU 26,27
Day	-21 to -1	1	8	15	22	1	8	15	22	1	8	15	22					1	8	15	22		
Adverse Events ¹⁸		X																					
									Trea	tme	nt Scl	hedule	!										
Elotuzumab ¹⁹		X	X	X	X	X		X		X		X						X					
Carfilzomib ²⁰		X	X	X		X	X	X		X		X											
Lenalidomide ^{21,22}												Da	ys 1-2	l									
Dexamethasone ^{23,24}		X 23	X 23	X 23	X 23	X 24	X 24	X 24	X 24	X 24	X 24	X 24	X 24					X 2 4	X 24	X 24	X 24		

(X) As clinically indicated

- 1. Informed consent may be obtained within 30 days of start of treatment but must be obtained prior to any research-related activity
- 2. Includes baseline symptoms, neuropathy history and documentation of the CTCAE grade if peripheral neuropathy is present at baseline.
- 3. May be within 3 months of planned start. Includes: lateral radiograph of skull, anteroposterior and lateral views of the spine, and anteroposterior views of the pelvis, ribs, femora, and humeri. Skeletal surveys performed outside of the 30-day window may be considered for inclusion after discussion with the Lead Principal Investigator. Skeletal survey only needs to be repeated throughout the trial if clinically indicated.
- 4. 12-Lead ECG including QTc interval. ECG should be performed throughout the study only as clinically indicated
- 5. Echocardiogram must be completed at screening to demonstrate LVEF ≥ 50%. ECHO may be performed throughout the study if clinically indicated.

- 6. For Day 1 of cycle 1, screening results may be used if within 7 days of treatment start. Complete physical exam (including vital signs, [systolic and diastolic blood pressure, respiration, pulse, oral temperature], height, weight, calculation of body surface area [BSA]) and ECOG score required at screening at Day 1 of each cycle (height only required at screening). Symptom-directed Physical Exam on Days 8, 15, (and 22 on cycles 1-2)
- 7. Systolic and diastolic blood pressure, pulse, respiration, temperature before and after elotuzumab infusion and approximately 1 hour before carfilzomib dosing on days where only carfilzomib is dosed.
- 8. Hemoglobin, WBC with complete differential, RBCs, platelet count, absolute neutrophil and lymphocyte counts. Results must be reviewed before dosing. On cycles 1-8, these tests will be required on days 1, 8, and 15 prior to infusion and on cycles 9+ they will be required on days 1 and 15 prior to infusion.
- 9. Full serum chemistry panel at screening, days 1, 8, and 15, and EoT for all subjects: sodium, potassium, chloride, creatinine, glucose, uric acid, phosphorus, magnesium, LDH, total bilirubin, C-Reactive Protein. Results must be reviewed before dosing. On cycles 1-8, these tests will be required on days 1, 8, and 15 prior to infusion and on cycles 9+ they will be required on days 1 and 15 prior to infusion.
- 10. Pregnancy tests must occur within 10-14 days and again within 24 hours prior to prescribing lenalidomide (prescriptions must be filled within 7 days. FCBP with regular or no menstruation must have a pregnancy test weekly for the first 28 days and then every 28 days while on therapy (including breaks in therapy); at discontinuation of lenalidomide and at Day 28 post the last dose of lenalidomide. Females with irregular menstruation must have a pregnancy test weekly for the first 28 days and then every 14 days while on therapy (including breaks in therapy), at discontinuation of lenalidomide and at Day 14 and Day 28 post the last dose of lenalidomide. When applicable, females must have a pregnancy test at the EoT.
- 11. Disease assessment including bone marrow biopsy (as indicated), SPEP, UPEP, SFLC to be done at any point during treatment when response is suspected. The first response assessment should be completed on Cycle 1 Day 15 and on D1 of every cycle onwards.
- 12. Obtain blood for M-protein levels measured by SPEP or quantitative immunoglobulins for those subjects in whom SPEP/UPEP are felt to be unreliable (IgA type multiple myeloma), depending upon which studies were positive at baseline. SPEP is required on Cycle 1 Day 15 for all subjects. A serum sample from blood at landmark timepoints (after C4, 8, 12, and 18, 24 months after C1D1, and yearly after) will be required for banking at the University of Chicago for later M-spike analysis with a new elotuzumab interference assay. BMS will perform this assay on banked samples, using using Mass Spectrometry.
- 13. Urine protein electrophoresis (UPEP), and urine protein immunofixation (only for those whose disease is being followed by UPEP). Subjects with baseline urine protein greater than 200 mg/24 hours must have a UPEP to confirm VGPR or better. For subjects whose disease is being monitored through UPEP, additional post baseline 24-hour urine collections are required as indicated. UPEP is required on Cycle 1 Day 15 for all subjects.

- 14. 24 hour urine is required on Cycle 1 Day 15 for all subjects.
- 15. Bone marrow aspirate and biopsy quantify % myeloma cell involvement; bone marrow sample for cytogenetics and fluorescent in situ hybridization (FISH). Repeat bone marrow biopsy/aspirate if nCR (or VGPR when nCR determination is not possible) is suspected and as appropriate to confirm achievement of sCR, CR, or nCR. Bone marrow biopsy/aspirate performed outside of the 30-day window may be considered for inclusion. Please contact the Lead Principal Investigator at the coordinating site on a case-by-case basis. Cytogenetics and FISH are required at screening only. If cytogenetics/FISH are completed at a time point other than screening, the results should be captured in eCRF.
- 16. All subjects are required to have a sample for MRD collected at screening, end of cycles 4, 8 12, 18 (if MRD+ at C8 but MRD- at C12), 24 months after C1D1, yearly after that, and at any other time a Bone Marrow biopsy/aspirate is collected as SOC. If nCR (or VGPR if nCR determination is not possible) is recorded between screening and EoT, a Bone Marrow Biopsy can be indicated. However, if nCR (or VGPR when nCR is not possible) is suspected within 2 months of a scheduled BM per protocol, it is acceptable to wait for the scheduled BM biopsy. Refer to lab manual for collection and shipping instructions. Central analysis includes MRD by multiparameter flow cytometry and MRD by gene sequencing. Non-decalcified FFPE or BMA slides from the subject at screening can be provided alternatively to fresh BM for calibration of MRD by gene sequencing.
- 17. For subjects who sign additional consent: peripheral blood and bone marrow aspirate samples collected at screening, end of cycle 4, 8, 12, and 18, 24 months after C1D1, yearly after that, and any time after enrollment that nCR or better is suspected or a BM is performed per protocol. Buccal mucosa swab will be collected at screening only. Please see the lab manual for specific instructions
- 18. AEs will be collected from the time of first study drug treatment through 30-days after end of study treatment.
- 19. Elotuzumab will be given IV at 10mg/kg weekly in 28-day cycles in cycles 1 and 2 starting on cycle 1 day 1. In cycles 3+, elotuzumab will dosed IV at 10mg/kg every two weeks in 28-day cycles starting on cycle 3 day 1. Refer to section 6.3.1 for elotuzumab infusion rates.
- 20. Carfilzomib days 1, 8, and 15 of cycles 1-8 and 1 and 15 of cycles 9+ at assigned dose. Cycle 1 step-up dosing is required: 20mg/m² Day 1; 56mg/m² Day 8; 56mg/m² Day 15. On Cycle 2 day 1, the dose of carfilzomib will be escalated to 70mg/m² and will continue to be dosed at this level. Hydration directions from section 6.3.2 must be followed
- 21. Lenalidomide must be prescribed through and in compliance with the RevlimidREMS™ program of Celgene Corporation. Prescriptions must be filled within 7 days. Consideration should be given to prescribing lenalidomide 5 to 7 days in advance of Day 1 of each cycle to allow time for required subject and prescriber surveys, and drug shipment to subject.

- 22. Lenalidomide dosing Days 1-21. Cycles 1-8 Lenalidomide will be administered at 25 mg. From cycle 9+ Lenalidomide will be administered at best tolerated dose on days 1-21 of a 28-day cycle. Lenalidomide should be taken in the evening at approximately the same time each day.
- 23. On cycles 1-2, dexamethasone will be split into two doses as follows: 20mg of dexamethasone will be given IV on days 1, 8, and 15 no more than 3 hours prior to elotuzumab infusion and between 30min and 4 hours prior to carfilzomib, and 20mg will be taken PO on days 2, 9, and 16. On Day 22 of cycle 1, 40mg dexamethasone will be taken PO no longer than 3 hours prior to elotuzumab. When dexamethasone, carfilzomib and elotuzumab coincide, dexamethasone will be dosed first, followed by carfilzomib infusion, and finally elotuzumab will be infused.
- 24. On cycles 3-4 40mg dexamethasone will be taken PO on days 1, 8, 15, and 22. On days when dexamethasone coincides with elotuzumab, dexamethasone will be taken no longer than 3 hours prior to elotuzumab infusion. On days when dexamethasone coincides with carfilzomib, dexamethasone will be taken between 30min and 4 hours prior to carfilzomib infusion. When dexamethasone, carfilzomib and elotuzumab coincide, dexamethasone will be dosed first, followed by carfilzomib infusion, and finally elotuzumab will be infused. On cycles 5+ 20mg dexamethasone will be taken PO on days 1, 8, 15, and 22. On days when dexamethasone coincides with elotuzumab, dexamethasone will be taken no longer than 3 hours prior to elotuzumab infusion. On days when dexamethasone coincides with carfilzomib, dexamethasone will be taken between 30min and 4 hours prior to carfilzomib infusion. When dexamethasone, carfilzomib and elotuzumab coincide, dexamethasone will be dosed first, followed by carfilzomib infusion, and finally elotuzumab will be infused.
- 25. End of treatment will vary depending on MRD results post cycle 8 and 12. Subjects that are MRD negative after cycle 8 and 12, will go on E-Rd maintenance until disease progression, subjects that are MRD+ after cycle 8 but MRD- after cycle 12, will get another 6 cycles of Elo-KRd and go on E-Rd maintenance until disease progression; and subjects that are MRD+ at both instances will be given another 12 cycles of Elo-KRd and go on E-Rd maintenance until disease progression
- 26. Subjects will be followed for survival and development of any new cancers, at least every 3 months for up to 6 years from start of treatment. Reports of any death should include date of death and specific cause (disease under study or specify other cause).
- 27. Assessment for disease progression in subjects who did not progress during treatment. Every 3 months (+/- 30 days) from safety follow-up visit (28 days post-last study treatment or ASCT, if applicable) for up to 6 years from enrollment.
- 28. A CT-PET must be performed to confirm MRD-negative disease per Standard of Care. Subjects who are MRD-positive do not need PET scans until suspected CR. MRD-negative subjects will undergo a yearly PET until progression. If there is clinical need for assessment at cycles 8 and 12, a CT-PET should be performed at these timepoints as well.

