6.2.2. Treatment Phase Procedures

The following assessments should be performed on Day 1 of each cycle before administering drug unless otherwise noted. Please refer to Appendix 4 for details of response evaluation to be completed at any time throughout the trial when a nCR (or VGPR when nCR determination is not possible) or better is suspected. Hematology and Chemistry labs are required per SOC before Carfilzomib infusion on day 1, 8, and 15 of cycles 1-8, and on days 1, and 15 of cycles 9+. On cycles 9+ this evaluation should be done as clinically indicated.

Complete Physical examination and vital signs on Day 1

- Body weight
- **BSA**
- **ECOG Performance Status**
- Blood pressure, pulse, temperature, respiration
- Physical examination
- Pulse oximetry to investigator discretion

Symptom-directed Physical Exam

Days 8, 15, (and 22 on cycles 1-2)

Vital signs on each treatment day with Carfilzomib and/or elotuzumab

Hematology

(Day 1,8 and 15 on cycles 1-8before infusion required. On cycles 9+ days 1 and 15 before infusion and as clinically indicated)

Complete clinical chemistry

(Day 1, 8, and 15 on cycles 1-8 before infusion required. On cycles 9+ days 8 and 15 before infusion and as clinically indicated)

Pregnancy Test

Myeloma Disease Assessment – laboratory

(Cycle 1 Day 15 and on Day 1 of every cycle from cycle 2+)

Hemoglobin, WBC with complete differential, RBCs, platelet count, absolute neutrophil and lymphocyte counts. WBC differential may be automated or manual as per institutional standards. Results must be reviewed before dosing.

Sodium, potassium, chloride, creatinine, glucose, uric acid, phosphorus, magnesium, LDH, total bilirubin, CRP Results must be reviewed before dosing in Cycles 1 and 2.

FCBP with regular or no menstrual cycles must agree to have pregnancy tests every 7 days (weekly) for the first 28 days of study participation and then every 28 days while on study. If menstrual cycles are irregular, the pregnancy testing must occur weekly for the first 28 days and then every 14 days while on study.

M-protein determination:

- Serum Protein Electrophoresis (SPEP) and immunofixation
- Urine Protein Electrophoresis (UPEP) and immunofixation
- 24hr Urine
- Serum Free Light Chains
- Serum quantitative immunoglobulins (Igs)

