6.2.3. End of Treatment Procedures and Long-Term Follow-Up

Subjects who discontinue therapy for any reason must have and end of treatment (EOT) visit completed 30 days (± 7 days) after the last application of study drug. Following the end of treatment, subjects will be followed for survival for 6 years total since enrollment.

At the EOT visit, the subjects will undergo the following assessments:

Physical examination and vital

signs

- Body weight
- **ECOG**
- Blood pressure, pulse, temperature, respiration
- Physical examination

Pulse oximetry to investigator discretion

Hematology Hemoglobin, WBC with complete differential, RBCs,

> platelet count, absolute neutrophil and lymphocyte counts. WBC differential may be automated or manual as per

institutional standards.

Clinical chemistry Sodium, potassium, chloride, creatinine, glucose, uric

acid, phosphorus, magnesium, LDH, total bilirubin, CRP

Pregnancy test (if applicable) testing required **FCBP** pregnancy at treatment

> discontinuation and at 28-days following treatment discontinuation. If menstrual cycles are irregular, 14-days additional testing following treatment

discontinuation is required

Myeloma Disease Assessment-

laboratory

M-protein determination:

Serum Protein Electrophoresis (SPEP) and

immunofixation

- Urine Protein Electrophoresis (UPEP) and immunofixation
- 24hr Urine
- Serum Free Light Chains
- Serum quantitative immunoglobulins (Igs)

Bone Marrow Aspirate/biopsy

All BM aspirates and biopsies are SOC, except the end of cycle 4 sample, which will only be SOC for subjects who proceed to transplant. Quantify percent myeloma cell involvement, and obtain bone marrow aspirate for MRD analysis by flow and NGS. This is required at EOT (C12, C18 or C24), 24 months after C1D1, and yearly after that (for up to 6 years after enrollment). Additionally, a BM aspirate and biopsy is required at any time nCR is suspected and MRD will be tested at this time. If nCR (If nCR determination is not possible, then VGPR will be used to trigger a bone marrow biopsy. A Bone Marrow Biopsy to confirm nCR or VGPR will not be required if the subject is within 2 months of a landmark Bone Marrow Biopsy timepoint) is suspected within 3 months of EOT, it is acceptable to wait for the EOT BM biopsy.

For subjects who sign consent for correlative samples, an additional aspirate sample should be collected at EOT

CT-PET

MRD-negative subjects will undergo a yearly PET until

progression.

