Heart problems, including rapid, strong, or irregular heartbeat, heart attack, reduced blood flow to the heart, abnormal amount of fluid to the lining around the heart, and swelling/irritation of the lining around the heart	NA	≥ Grade 3: Carfilzomib attribution, hold drug until resolved to ≤ Grade 1. Resume at one level dose reduction	NA
Pericardial Effusion	NA	≥ Grade 3: Carfilzomib attribution, hold drug until resolved to Grade 1. Resume at one level dose reduction	NA
Pericarditis	NA	≥ Grade 3: Carfilzomib attribution, hold drug until resolved to Grade 1. Resume at one level dose reduction	NA
Pulmonary Hypertension	NA	≥ Grade 3: Carfilzomib attribution, hold drug until resolved to baseline. After resolution consider if restarting CFZ at the same dose or reduced dose is appropriate. If tolerated, the reduced dose may be escalated to the previous dose at the discretion of the physician.	NA
Pulmonary Toxicities: Interstitial Lung Disease (inc. pneumonitis), Acute Respiratory Failure, and Adult Respiratory Distress Syndrome (ARDS), cough and cough with phlegm	NA	 ≥ Grade 2 for Pneumonitis ≥ Grade 3 for ARDS ≥ Grade 4 for Respiratory Failure Carfilzomib attribution, hold drug until resolved to ≤Grade 1. Resume at one level dose reduction 	NA

Table 6-6 Dose Modifications for Non-hematologic Toxicity

Recommended Action			
Non-heme toxicity	Lenalidomide	Carfilzomib	Elotuzumab
Blood clot in the lungs, fluid in the lungs, bleeding in the lungs	NA	≥ Grade 3: Carfilzomib attribution, hold drug until resolved to ≤ Grade 1. Resume at one level dose reduction	NA
Gastrointestinal Perforation	NA	≥ Grade 3: Carfilzomib attribution, hold drug until resolved to Grade 1. Resume at one level dose reduction	NA
Hepatic Toxicities (≥ Grade 3 elevation of AST or ALT, Bilirrubin, or other ≥ Grade 3 liver abnormalities)	Hold drug until resolved to ≤Grade 1 or baseline. Resume at the same dose or reduced dose as appropriate. If tolerated, the reduced dose may be escalated to the previous dose at the discretion of the physician. Frequent monitoring of liver function should then be implemented.	Hold drug until resolved to ≤Grade 1 or baseline. Resume at the same dose or reduced dose as appropriate. If tolerated, the reduced dose may be escalated to the previous dose at the discretion of the physician. Frequent monitoring of liver function should then be implemented.	Hold treatment and restart when toxicity has resolved to ≤ Grade 1 or baseline

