- any laboratory abnormality that required the subject to receive specific corrective therapy.

Potential Drug Induced Liver Injury (DILI)

Wherever possible, timely confirmation of initial liver-related laboratory abnormalities should occur prior to the reporting of a potential DILI event. All occurrences of potential DILIs, meeting the defined criteria, must be reported as SAEs. Potential drug induced liver injury is defined as:

- 1) ALT or AST elevation > 3 times upper limit of normal (ULN) AND
- Total bilirubin > 2 times ULN, without initial findings of cholestasis (elevated serum alkaline phosphatase)
 AND
- 3) No other immediately apparent possible causes of AST/ALT elevation and hyperbilirubinemia, including, but not limited to, viral hepatitis, pre-existing chronic or acute liver disease, or the administration of other drug(s) known to be hepatotoxic.

Overdose

An overdose is defined as the accidental or intentional administration of any dose of a product that is considered both excessive and medically important. All occurrences of overdose must be reported as an SAE.

Other Safety Considerations

Any significant worsening noted during interim or final physical examinations, electrocardiograms, x-rays, and any other potential safety assessments, whether or not these procedures are required by the protocol, should also be recorded as a nonserious or serious AE, as appropriate, and reported accordingly.

Unexpected AEs

An unexpected AE is any adverse drug event, the specificity or severity of which is not consistent with the current IB or prescribing information for a marketed compound. Also, reports which add significant information on specificity or severity of a known, already documented AE constitute unexpected AEs. For example, an event more specific or more severe than described in the IB would be considered "unexpected".

Whenever possible, the Common Terminology Criteria for Adverse Events (CTCAE) version 4.0 should be used to describe the event and for assessing the severity of AEs (see Appendix 3). Any events representing a change in the CTCAE Grade need to be reported on the AE case report form. This includes any change in laboratory values.

For AEs not adequately addressed in the CTCAE, the severity table below may be us	For AEs r	ot adequately	addressed in	the CTCAE.	the severity	v table below may	v be used:
---	-----------	---------------	--------------	------------	--------------	-------------------	------------

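### The on-treatment and end-of-treatment chemistry lists omit AST, ALT, alkaline phosphatase and calcium, although dose-modification, safety and response rules depend on them

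*Combined protocol and SAP*

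**What the plan says.** Appendix 6 footnote 9 sets the scope as "Full serum chemistry panel at screening, days 1, 8, and 15, and EoT for all subjects" and then gives the content: "sodium, potassium, chloride, creatinine, glucose, uric acid, phosphorus, magnesium, LDH, total bilirubin, C-Reactive Protein". Section 6.2.2 repeats the list for the treatment phase; as extracted, it ends "phosphorus, magnesium, LDH, total bilirubin, CRP Results must be reviewed before dosing in Cycles 1 and 2". Section 6.2.3 repeats it for the end-of-treatment visit, ending "acid, phosphorus, magnesium, LDH, total bilirubin, CRP". The screening list in 6.2.1 is the same.

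Section 6.2.2 also says that "Hematology and Chemistry labs are required per SOC before Carfilzomib infusion", without naming any analyte.

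Other parts of the protocol act on tests that are not in these lists:

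- Table 6-6 has a hold rule headed "Hepatic Toxicities (≥ Grade 3 elevation of AST or ALT, Bilirrubin, or other ≥ Grade 3 liver abnormalities".
- Section 8 defines potential DILI, a mandatory SAE, by "ALT or AST elevation > 3 times upper limit of normal (ULN" together with "Total bilirubin > 2 times ULN, without initial findings of cholestasis (elevated serum alkaline phosphatase" and the absence of another evident cause.
- Appendix 4 counts disease-related hypercalcaemia, with corrected calcium above 11.5 mg/dL, as progression, and requires a normal calcium for nCR.
- Section 6.10.3 names a calcium fall of at least 20% among the pre-dose findings that bar a dose in Cycles 1 and 2.

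**The concern.** A site that runs exactly the panel the protocol calls full has no transaminase value with which to apply the AST/ALT limb of the hepatic hold rule, and no calcium value with which to apply the hypercalcaemia limb of progression. Whether these tests are done then depends on local ordering at each of the five centres (4.2.2).

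Three things are at stake. The first is patient safety: a Grade 3 transaminase rise without raised bilirubin would not show on the listed panel. The second is the safety analysis, a secondary endpoint. Section 8.2 has every Grade 3-4 laboratory abnormality recorded as an adverse event, but an analyte that is not measured cannot yield one, so rates for these analytes could differ between centres because of testing practice. The third is response and progression: calcium enters one route to progression, and hence PFS, time to progression and duration of response, and it enters the nCR definition behind the nCR-or-better rate in 10.2.2.

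**Working it through.** No design figure is involved, so the check compares lists with rules.

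**Step 1: the panel.** Footnote 9 lists sodium, potassium, chloride, creatinine, glucose, uric acid, phosphorus, magnesium, LDH, total bilirubin and CRP, which makes 11. Sections 6.2.1, 6.2.2 and 6.2.3 give the same 11. Four matching lists make a loss in PDF extraction implausible.

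**Step 2: rules against the panel.**

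| Rule | Listed inputs | Unlisted inputs |
|---|---|---|
| Hepatic row, Table 6-6 | total bilirubin | AST, ALT |
| Hypercalcaemia progression, Appendix 4 | none | calcium |
| nCR, calcium component, Appendix 4 | none | calcium |
| Cycle 1-2 pre-dose check, 6.10.3 | creatinine, LDH, uric acid, phosphate, potassium | calcium |
| Potential DILI, Section 8 | total bilirubin | AST/ALT, alkaline phosphatase |

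**Step 3: does another section supply the missing tests?**

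- The disease-assessment lists in 6.2.2, 6.2.3 and 6.7 cover serum and urine M-protein, free light chains and immunoglobulins. None includes calcium.
- Sections 6.4.2 and 6.10.4 require chemistry before each carfilzomib dose in Cycles 1 and 2, but name only creatinine.
- Section 6.10.3 presupposes a calcium value in Cycles 1 and 2, but adds calcium to no list.
- Section 6.10.2 asks that significant electrolyte disturbances be corrected before carfilzomib, and names no electrolyte.
- The hepatic row of Table 6-6 asks for frequent liver-function monitoring, but only after a hepatic event has been found.
- Sections 5.1 and 5.2 set limits for AST/ALT and corrected calcium. These force the tests at screening only.

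No section therefore schedules AST, ALT or alkaline phosphatase for first detection on treatment or at end of treatment, and no section lists calcium there.

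**Step 4: how the DILI definition works.** Its criteria are joined by AND. Bilirubin above 2 times ULN is a necessary condition and is on every panel. A DILI case at a scheduled draw would therefore show one listed abnormality; AST/ALT and alkaline phosphatase would still be needed to classify it.

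**Step 5: reach into efficacy.** Stringent complete response (sCR), complete response and MRD status use none of the four analytes, so the primary endpoint is untouched. M-protein and free light chains are assessed on Day 1 of every cycle from Cycle 2, so most progression has another route to detection. Calcium can change the nCR-or-better rate only for subjects at exactly nCR. The marrow trigger falls back to VGPR when nCR cannot be determined.

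**The case against.** The best defence is that this is incomplete specification and not a contradiction. No list forbids other tests, chemistry is tied to standard of care, and sites treating myeloma with these drugs may well measure liver enzymes and calcium anyway. Bilirubin keeps part of the hepatic rule working, and Sections 8 and 8.2 already call for laboratory results and Grade 3-4 abnormalities to be recorded. Part of this stands: local practice and the case report form are not in the documents, so no missed event can be shown. It does not close the gap, because the standard-of-care sentence names no analyte, while footnote 9 presents its list as the full panel for all subjects.

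A reader might infer three stronger points that the documents do not support:

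- **A missed transaminase rise is a missed DILI report.** An isolated rise cannot meet the definition, which also requires the raised bilirubin that every panel measures. Such a rise bears on Table 6-6 and on Grade 3-4 laboratory recording.
- **Calcium is plainly ignored, or plainly covered, in Cycles 1 and 2.** Neither holds: 6.10.3 relies on a value that no list supplies.
- **The number of scheduled draws measures the harm.** A count would show how often the wording applies, not what was missed. It would also be uncertain, because 6.2.2 and footnote 9 disagree on chemistry days from Cycle 9 onward.

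**Conclusion.** The concern holds as an inconsistency between the chemistry lists and the rules that use them. All four analytes are absent from all three on-treatment and end-of-treatment lists. The main gaps are AST/ALT for the hepatic row of Table 6-6, and calcium for hypercalcaemia progression, nCR and the 6.10.3 check. The DILI link is secondary.

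The consequence is a risk of uneven detection and uneven safety data between centres. Its size cannot be estimated from the documents. The judgement that the effect on PFS and the nCR rate is probably small assumes that most progression shows in M-protein or free light chains, and that few assessments turn on calcium alone. The point should be corrected, but it does not threaten the primary analysis.

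**What to change.** Reconcile the lists in 6.2.2, 6.2.3 and Appendix 6 footnote 9 with Table 6-6, Section 8, 6.10.3 and Appendix 4, and align 6.2.1 for consistency. Either of two wordings would do, both at draws already scheduled:

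- name AST, ALT, alkaline phosphatase and calcium in the lists; or
- state expressly that local standard of care must supply these four tests and that the results are recorded for the study.

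No threshold, dose or management rule needs to change. The cost is a short amendment at four places and slight added laboratory and data-entry work, with no extra blood draws.
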